5.1.2.1 Secondary Endpoints

- Change in UUI episodes at 6 months compared to baseline in subjects with UUI at baseline
- Change in daily UF episodes at 6 months compared to baseline in subjects with UF at baseline
- Change in urinary urgency assessed through the UPS at 6 months compared to baseline
- Change in OAB-q HRQL (health related quality of life) Total Score at 6 months compared to baseline

6. Study Design

This is a prospective, multicenter, pivotal study to assess safety and efficacy for the implantable TNM device in subjects with overactive bladder.

Eligible subjects will sign a study-specific informed consent form (ICF), at which time they will be considered enrolled in the study. All eligible subjects will complete baseline procedures, including a baseline diary and assessment of medical history. Subjects must be consented and meet all inclusion and no exclusion criteria to continue to the neurostimulator implant procedure. Any subject who does

not meet all inclusion/exclusion criteria will be excluded from study participation and exited from the study.

Study requirements, including diaries, questionnaires and safety assessments will be completed as required in Section 10. Subject follow-up is expected to last approximately 24 months following the neurostimulator implant procedure. Subjects will be exited from the study after the 24-month follow-up visit is completed. Any subjects who have the device explanted and not replaced during follow-up will be exited from the study.

The study is expected to be conducted at up to 30 study sites located in the United States. Up to 200 subjects will be enrolled to obtain 121 subjects who have the study device implanted. Enrollment will be closed once the number of completed implants reaches 121; all enrolled subjects who meet eligibility criteria may be implanted (not to exceed 130 total implants).

To ensure a widespread distribution of data and minimize study site bias in study results, the maximum number of subjects to be implanted at a single study site is 24 subjects.

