accordance with device instructions and documented on the programming worksheet prior to the explant (when possible) and at the time of any new implant procedures. The therapy schedule will be set based on the timeframe in the study when the system modification was completed, and the therapy session may be initiated during the visit or within 24 hours.

Post-operative instructions should be followed for any replacement neurostimulators. Following a system modification, the subject should complete a 7-day post procedure visit. In addition, the subject will receive a 1-month post-procedure call in order to assess compression, wound healing, activity levels, etc. The subject will then continue their follow-up schedule based on the initial device implant date.

Post-operative instructions should be followed for any device explant which is not associated with a device replacement procedure. The subject will receive a 1-month phone call in order to confirm resolution of any ongoing adverse events. It is recommended to follow the subject until all ongoing related AEs are resolved or unresolved with no further actions planned.

No replacement neurostimulators will be provided after participation in the study has ended.

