14.4 Primary Objective

14.4.1 Primary Objective – UUI Responder Rate

To demonstrate that the percentage of subjects who are considered a UUI responder after 6 months of tibial neuromodulation exceeds a performance goal of 40%.

Hypothesis: The percentage of subjects who are considered an UUI responder 6 months after tibial neuromodulation implantation is greater than 40%.

$H_0: p \leq 40\%$

$H_A: p > 40\%$

Where p = the percentage of subjects who are UUI responders

Endpoint Definition and Derivation: A 3-day urinary voiding diary be used to collect bladder symptoms, including UUI episodes. The primary objective endpoint is the proportion of tibial neuromodulation subjects considered a UUI responder at 6 months after device implant. A subject is considered a UUI responder if they meet the UUI responder criteria as defined in the voiding diary analysis section 14.1.5.

Performance Requirements: The null hypothesis will be rejected if the two-sided p-value is less than 0.05.

Rationale for Performance Criteria: The proposed study design includes a primary objective performance goal of 40%. The performance goal defines an active historical control for this study and

was defined to position the outcome between the expected performance for medications and the more complex SNM treatment.

Sample Size Justification: The sample size justification for the primary objective is provided in section 14.7.

Analysis Methods: The analysis for UUI responder rate will be summarized at 6 months after implant. If 5% of the data or fewer are missing for the primary analysis, no imputation will be used and the objective will be tested using a binomial test for the Complete Case analysis set. Otherwise, missing data will be imputed for the Full Analysis Set as specified in section 14.1.2, and the objective will be tested using a Z-test. The two-sided 95% confidence interval will also be provided.

Determination of Subjects/Data for Analysis: The primary objective analysis will include all subjects from the Full Analysis Set (i.e., all implant attempted subjects) as defined in section 14.1.1.

Supportive and Sensitivity Analyses: There are no requirements or expectations for the results of the supporting and sensitivity analyses. They are meant to investigate the robustness of the study results and/or to provide further details on the therapy effects.

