### **7.1.3 Analysis Sets**

All Enrolled analysis set: Includes subjects who completed the informed consent process.

Full Analysis Set (FAS): Includes subjects with an attempted implant. If all implant procedures are successful, this will be equivalent to the All Implanted Analysis set. In the case that all subjects have successful implant procedures, the name 'All Implanted Analysis set' will be used. This is the primary analysis set for both safety and effectiveness .

All Implanted Analysis set: Includes subjects who are implanted.

Complete Case analysis sets: Includes subjects who are implanted and provide outcome measures at both baseline and follow-up visits. This set is defined for each outcome measure at each follow-up visit.

As Treated analysis sets: Includes only those complete case subjects who received stimulation in the period prior to the visit. This set is defined for each outcome measure at each follow-up visit. Subjects will be excluded from the As Treated analysis sets if they meet 1 or more of the following:

- If the subject received zero therapy sessions in the 2 weeks prior to the visit
- If the subject experienced a consecutive 4 week period with zero therapy sessions in the 3 months prior to the visit.

**Note:** In the case of missing daily usage data, all missing usage days will be considered as days where the subject received a therapy session as expected per their current program (i.e., missing usage data will not contribute to meeting the 2 criteria above).

The study requires subjects to have diagnosed UUI to be implanted. For analysis purposes, Urinary Frequency (UF) subjects are those who have  $\geq 10$  urinary frequency episodes per day at baseline and all subjects will be considered to have urinary urgency since all eligible subjects have UUI.

Some supportive, secondary objective, [REDACTED] may use different definitions or subsets of the analysis sets listed above (e.g., changed assumptions for those subjects considered to have either UUI or UF).

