## 7.2 General Methodology

The study will be considered successful when the primary objective is met. To support an indication for OAB, device therapy effectiveness will be demonstrated for the symptoms associated with OAB, including UUI, UF, and urgency.

For each of the objectives, the available data will be summarized, and missing data will be discussed. The main analysis of the study objectives will be intention-to-treat, meaning that the analysis will use the Full Analysis Set (FAS). The FAS includes all subjects, using the intention-to-treat (ITT) principle, who have an attempted device implant. Additional information on missing data plans are found in section 7.4.

Analyses of all data will be summarized with standard descriptive summary statistics, including counts and percentages for categorical variables, and mean, standard deviation, median, minimum, and maximum for continuous variables. The primary objective will be tested as described in section 7.9.1.1. If the primary objective is passed, the secondary objectives will each be tested as described in section 7.9.2 following the Hochberg multiple testing strategy. All p-values will be reported as 2-sided tests. Additionally, 95% Confidence intervals will be supplied for selected measures.

Safety data will be summarized as the count of events, count of subjects, and percentage of subjects who experienced the event. Subject disposition will be illustrated in a flow diagram. Subject visits will be tabulated and compliance to the visit schedule and visit windows will be summarized. Attrition will be identified and summarized, including the number and causes of death if any occur in the study.

Data analysis will be performed by Medtronic-employed statisticians or designees. A validated statistical software package (e.g., SAS version 9.4 or higher) will be used to analyze the study results. PASS 2019 sample size calculation software was utilized for determination of sample sizes and associated statistical power calculations.

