## **7.4 Handling of Missing, Unused, and Spurious Data and Dropouts**

Primary and secondary objectives will be analyzed using the FAS. The FAS includes all subjects, using the intention-to-treat principle, who have an attempted device implant. All attempts will be made to minimize missing data. For diary-based metrics, missing is defined as any diary which has a total length of less than 48 hours, as defined in section 7.2.2. The OAB-q may be missing if the HRQL Total cannot be calculated; scoring details are found in section 7.9.2.4. If 5% of the data or fewer are missing for the analysis, no imputation will be used, and the data will be analyzed using the Complete Case analysis set (Buhi 2008). Otherwise, if missing data are observed, imputation will be used for the primary and secondary objectives.

The primary objective imputation will be done using multiple imputation (MI). Predictive mean matching multiple imputation will be used for each variable. First, multiple imputation will be applied to impute missing values in average daily UUI episodes. Unless model errors dictate otherwise, each model will consider Baseline and Month 1, Month 2, Month 3, and Month 6 variables for the UUI episodes variable and demographic variables of age, gender, history of pregnancy, and BMI. The fully conditional specification (FCS) method within SAS (version 9.4 or higher) with 30 repetitions and 100 burn-in iterations will be used for imputation. No limits will be defined for imputed values. Following

imputation, the 6-month outcome data will be converted to the appropriate endpoint (i.e., change from baseline/UUI responder). The estimate and variance of the mean proportion of subjects considered a UUI responder will be determined for each imputation dataset. For the primary objective, the mean and variance for the proportion will be determined using MI analysis methods and the objective will be tested using a Z-test comparing the observed responder rate to the primary objective performance goal of 40%.

For the UUI, UF, and OAB-Q secondary objectives, the following imputation steps will be taken:

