## 7.9 Evaluation of Objectives

### 7.9.1 Primary Objective

#### 7.9.1.1 Primary Objective – UUI Responder Rate

To demonstrate that the percentage of subjects who are considered a UUI responder after 6 months of tibial neuromodulation exceeds a performance goal of 40%.

**Hypothesis:** The percentage of subjects who are considered a UUI responder 6 months after tibial neuromodulation implantation is greater than 40%.

$$H_0: p \leq 40\%$$

$$H_A: p > 40\%$$

Where  $p$  = the percentage of subjects who are UUI responders

**Endpoint Definition and Derivation:** A 3-day urinary voiding diary will be used to collect bladder symptoms, including UUI episodes. The primary objective endpoint is the proportion of tibial neuromodulation subjects considered a UUI responder at 6 months after device implant. A subject is considered a UUI responder if they meet the UUI responder criteria as defined in the voiding diary analysis section 7.2.2.

**Performance Requirements:** The null hypothesis will be rejected if the one-sided p-value is less than 0.025. Only the two-sided p-value will be reported.

**Rationale for Performance Criteria:** The proposed study design includes a primary objective performance goal of 40%. The performance goal defines an active historical control for this study and was defined to position the TNM outcome between the expected performance for medications and the more complex SNM treatment.

**Sample Size Justification:** The sample size justification for the primary objective is provided in section 6.

**Analysis Methods:** The analysis for UUI responder rate will be summarized at 6 months after implant. If 5% of the data or fewer are missing for the primary analysis, no imputation will be used, and the objective will be tested using a binomial test for the Complete Case analysis set. Otherwise, missing data will be imputed for the Full Analysis Set as specified in section 7.4, and the objective will be tested using a Z-test. The two-sided 95% confidence interval will also be provided.

**Determination of Subjects/Data for Analysis:** The primary objective analysis will include all subjects from the Full Analysis Set (i.e., all implant attempted subjects) as defined in section 7.1.3.

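### The primary analysis is labelled intention-to-treat on all implant-attempted subjects, but at 5% or less missing it tests a set without failed implants and early unreplaced explants; if these are non-responders, the 2.5% level is exceeded from two such subjects at N=121

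*SAP*

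**What the plan says.** **Stated population.** SAP 7.2 calls the main analysis intention-to-treat on the FAS. SAP 7.9.1.1 repeats this under the subjects for analysis: "The primary objective analysis will include all subjects from the Full Analysis Set (i.e., all implant attempted subjects". Protocol 14.1 and 14.4.1 agree.

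**Population tested.** Under Analysis Methods in the same SAP section, if 5% of the data or fewer are missing, "no imputation will be used, and the objective will be tested using a binomial test for the Complete Case analysis set". Protocol 14.4.1 has the same rule: "no imputation will be used and the objective will be tested using a binomial test for the Complete Case analysis set". SAP 7.1.3 defines the set: "Complete Case analysis sets: Includes subjects who are implanted and provide outcome measures at both baseline and follow-up visits".

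**Explants.** Protocol section 6: "Any subjects who have the device explanted and not replaced during follow-up will be exited from the study". Protocol 10.14.1 adds that nothing is collected after exit. Subjects whose device is replaced stay in: "The subject will then continue their follow-up schedule based on the initial device implant date" (Protocol 10.1, System Modification). Under Protocol 10.8, exit after an unreplaced explant follows a 1-month call, so a late explant may still leave a 6-month diary.

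**Above 5% missing.** SAP 7.4 imputes UUI episodes on the FAS from the diary visits, using "variables for the UUI episodes variable and demographic variables of age, gender, history of pregnancy, and BMI". The model has no term or assigned outcome for a failed implant or an explant.

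**Sensitivity analyses.** Complete Case, As Treated, All Implanted and tipping-point analyses are planned. SAP 7.9.1.1 attaches no requirement to their results.

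**The concern.** The trial has one arm, and success is a single test of the UUI responder rate against 40%. In the 5%-or-less branch, a failed implant is excluded by definition. An unreplaced explant who exits before the 6-month diary leaves both numerator and denominator. These subjects may well have had no benefit, yet neither document gives them an outcome. If they count as failures, the test is run on a group whose responder rate is higher than that of the FAS population the plan names, and it can declare success where the FAS result would not. Which of the two populations decides the trial then depends on a missing-data threshold.

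**Working it through.** **Inputs.** Performance goal 40%, one-sided alpha 0.025 (SAP 7.9.1.1). Planning rate 55%, N=121 implant-attempted, power at least 90% (SAP 6). Missing limit 5% (SAP 7.4). The number of dropped subjects, m, and their response rate are not given, so both are varied as assumptions.

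**Reproducing the plan.** The test is taken as the exact binomial: reject at the smallest r with P(X ≥ r | n, 0.40) < 0.025. At n=121, r=60, the size is 2.04% and power at 55% is 90.1%. This matches SAP 6.

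**Branch limit.** 6/121 = 4.96% stays in the branch; 7/121 = 5.79% leaves it.

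**Level with m dropped.** Fix the true FAS rate at 40%, so expected responders are 0.40 × 121 = 48.4. The evaluable rate is then:
- dropped are non-responders: 48.4/(121 − m); for m=6, 48.4/115 = 0.4209
- dropped respond at half the evaluable rate: 48.4/(121 − m/2); for m=6, 48.4/118 = 0.4102
- dropped respond like the rest: 0.40

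The level is P(X ≥ r | 121 − m, that rate).

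| m | n tested | r | Non-responders | Half rate | Same rate |
|---|---|---|---|---|---|
| 0 | 121 | 60 | 2.04% | 2.04% | 2.04% |
| 1 | 120 | 60 | 2.01% | 1.84% | 1.67% |
| 2 | 119 | 59 | 3.05% | 2.56% | 2.14% |
| 3 | 118 | 59 | 3.01% | 2.30% | 1.76% |
| 4 | 117 | 58 | 4.45% | 3.18% | 2.25% |
| 5 | 116 | 58 | 4.40% | 2.87% | 1.84% |
| 6 | 115 | 57 | 6.36% | 3.92% | 2.36% |

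The steps arise because the required count falls by one for every two subjects lost.

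**Failed attempts on top of 121 implants.** Enrolment closes on completed implants, so failed attempts may add to the 121. The test is then 60/121 while the FAS is 121 + k, and the evaluable rate is 0.40 × (121 + k)/121. If the k subjects are non-responders, the level is 2.44% (k=1), 2.91% (2), 3.44% (3) and 5.52% (6).

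**One data set, two answers.** 57/115 = 49.6% passes (p=0.024). The same 57 responders out of 121 are 47.1% and fail (p=0.067).

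**The case against.** The switch is openly pre-specified and worded alike in both documents. The endpoint is written for TNM subjects 6 months after implant, so the outcome of someone never implanted is undefined, not a known failure. The excess depends on an outcome that the plan does not assign. This stands, and it is why the claim is conditional.

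The large figures are corner cases. Reaching 6.4% needs exactly six drops, all failures, and no other missing diary, since other missing diaries use up the same 5%. The only explant rate in the documents, 2.2% for migration (Protocol 11.3), gives a level of about 3.1–3.2% if every such explant is unreplaced and has no diary, and 2.4–2.5% if half are. Under Binomial(121, 0.022), six drops has a probability of about 3%. This also stands.

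The planned sensitivity analyses, the tipping-point analysis above all, would probably show a discordant result. But none decides success. In this branch the Complete Case analysis is the primary analysis itself, and the All Implanted analysis also omits failed implants.

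A reader might infer more than the documents support:
- **That the trial's error rate is 6.4%.** No number of drops is given, and with 0 or 1 dropped within 121 there is no excess.
- **That the pausing rule (after 7 migration explants, and separately after 7 erosion explants) predicts up to six drops.** It counts events over all follow-up, replaced or not, and is not a forecast of missing 6-month diaries.
- **That every explant disappears.** Replaced subjects continue, and late explants may have a diary.
- **That the imputation branch is inflated too.** That depends on what the Month 1–3 diaries carry and was not established.

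**Conclusion.** The mismatch is real and can change the trial's only success decision. At N=121, if the dropped subjects are non-responders, the level stays at 2.0% with 0 or 1 dropped and exceeds 2.5% from two upward: about 3.0% (2–3), about 4.4% (4–5) and 6.4% (6, the most the branch allows). At half the evaluable response rate the excess is small or absent for two or three drops and reaches 3.9% at six. If dropped subjects respond like the rest, the level is at most 2.4%.

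The size rests on three assumptions: an exact test (the plan does not use the word, but the exact test reproduces its power), a true FAS rate of 40%, and a response rate among dropped subjects that is clearly below that of the others. The plan should be changed before the data are seen. Confidence in the contradiction is high; confidence in how large the excess would be in practice is limited.

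**What to change.** In SAP 7.4 and 7.9.1.1, and Protocol 14.1.2 and 14.4.1:

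1. Keep every failed implant, and every subject explanted without replacement before the 6-month assessment, in the primary denominator as a non-responder. Apply this at any missing fraction and whether or not a diary exists, so that the same event is always scored the same way.
2. In the 5%-or-less branch, keep the exact binomial test, on the FAS with this scoring. Leave other missing diaries to the existing 5% rule, with imputation above 5%. Do not move to the imputation Z-test because a few other diaries are missing: even with complete data, a Z-test at 40% has a size of 2.84% at N=125, and 3.13% at N=121 with the null variance.
3. Report the current Complete Case analysis as a sensitivity analysis. Add one that also scores all remaining missing FAS subjects as non-responders.
4. State in SAP 6 that 55% is the FAS rate, or restate power if it is the evaluable-subject rate. SAP 6 and Protocol 14.7 speak of implant-attempted subjects, but the Protocol synopsis speaks of implanted ones.

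**Effect.** With no other missing diaries, the level at N=121 is 2.04% with none of these subjects and 1.85% with six. Power stays at 90.1–90.8% if 55% is the FAS rate. If it is the evaluable-subject rate, power is about 0.86, 0.84 and 0.76 with 2, 3 and 6 such subjects within 121, against 0.90, 0.88 and 0.90 under the current rule.

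**Cost.** A somewhat stricter success test, possibly lower power, and a protocol amendment needing IRB approval and FDA approval as applicable (Protocol 16.6). No new data are needed, because implant outcome, explant, replacement and exit are already recorded.

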### 7.2.2 Diary Data Analysis

Several objectives [REDACTED] are based on the analysis of voiding diary data. The diary will be collected for 3 days prior to or after each study visit. The center will assign each diary to the corresponding visit in the eCRF. In some cases, the diary might be completed for slightly less or more than 3 days (e.g., for 68 or 75 rather than the expected 72 hours). All diaries which are greater than 48

hours will be used for analysis. For UI, UUI, and UF, the total number of episodes will be determined for each subject's diary collection period at each visit. UUI episodes are those leaks with urgency greater than none, urinary incontinence (UI) episodes are all leaks, and UF are all voiding episodes. The actual total length of the diary for each visit will be determined by using the subject-specific diary start and end time reported by the center. The number of episodes will be divided by the total length of the diary for that subject at the visit and reported as a daily (24 hour) rate (i.e., 'per day'). The change will be determined by subtracting the baseline value per day from the follow-up value per day. Percentage change will be determined by dividing the change in episodes per day by the baseline value. Negative values for change and percentage change represent an improvement. Responder rate for UUI is defined as the proportion of TNM subjects experiencing a reduction of 50% or more in daily UUI episodes. Responder rate for UF is defined as the proportion of TNM subjects experiencing a reduction of 50% or more in daily UF episodes or a return of voiding to <8 voids per day. Responder rate for UI is defined as the proportion of TNM subjects experiencing a reduction of 50% or more in daily UI episodes. Responder rate for UU is defined as the proportion of TNM subjects with an improvement of at least 1 point on the UPS. OAB responder rate is defined as the proportion of TNM subjects who are considered either a UUI, UF, or UU responder.

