**Supportive and Sensitivity Analyses:** There are no requirements or expectations for the results of the supporting and sensitivity analyses. They are meant to investigate the robustness of the study results and/or to provide further details on the therapy effects.

Additional supporting analyses to further understand the primary objective will be completed through analyses of the change in UUI (secondary objective) and percentage change in UUI (additional measure).

To assess the robustness of the primary objective results under the influence of missing data, sensitivity and subgroup analyses will be conducted using alternative missing data methods and by including different subsets of subjects. The first sensitivity analysis will be completed including subjects from the Primary Objective Complete Case analysis set. This analysis set will be used for a second sensitivity analysis which will be completed including only subjects who received stimulation ('As treated analysis') at the 6-month follow-up visit. An analysis will also be completed to evaluate UUI responder rate differences between different stimulation programs, comparing stimulation programs only if there are an adequate number of subjects in each stimulation program to ensure a stable estimate of response. A tipping point sensitivity analysis will also be completed. A final sensitivity analysis will be conducted on the Primary Objective Complete Case analysis set assigning response failure for the following subjects: those who took any dose of OAB medication in the 2 weeks prior to the diary collection period, and those who received an advanced therapy at any time from implant to the 6-month follow-up visit.

Complete Case analysis set subgroup analyses will be done for the following subject groups: sex, age (divided by median age; divided by age 65), race, and ethnicity. Subjects on the demographic cut point will be added to the adjacent group containing fewer subjects. Any subgroup with less than 10 subjects will not be reported.

As an exploratory analysis to assess if treatment effect differs by study center, a supporting analysis will be completed, as described in 7.3. This analysis will test whether the treatment effect is homogeneous between study centers for the UUI responder rate at 6 months.

UUI responder rate will be assessed over time through 24 months as part of the additional measures.

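### Month-6 UUI response is scored from the diary alone, so response on prohibited added OAB treatment can count towards the 40% goal; the SAP's existing failure rule belongs in the primary analysis

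*SAP*

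**What the plan says.** **Endpoint.** SAP 7.9.1.1 refers response wholly to the diary section: "A subject is considered a UUI responder if they meet the UUI responder criteria as defined in the voiding diary analysis section 7.2.2". SAP 7.2.2 then states: "Responder rate for UUI is defined as the proportion of TNM subjects experiencing a reduction of 50% or more in daily UUI episodes". Protocol 14.1.5 and 14.4.1 agree. Neither document makes response conditional on the absence of added OAB treatment. The main analysis is intention-to-treat on all subjects with an attempted implant (protocol 14.1, SAP 7.2), and the study succeeds when the primary objective is met.

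**Added treatment.** Protocol 10.1 and 10.5 prohibit OAB medication and additional advanced therapies for the first 12 months. If either is to be started, a voiding diary must first confirm non-response to tibial neuromodulation. The stated consequence of adding treatment before month 12 is a protocol deviation. SAP 7.1.2 summarizes deviations by type and centre.

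**Failure rule.** SAP 7.9.1.1 provides: "A final sensitivity analysis will be conducted on the Primary Objective Complete Case analysis set assigning response failure for the following subjects". One group is defined by medication: "those who took any dose of OAB medication in the 2 weeks prior to the diary collection period". The other group is anyone given an advanced therapy between implant and month 6. Protocol 14.4.1 has the same analysis but counts medication over the whole period from implant to the 6-month visit. On all such analyses the SAP says: "There are no requirements or expectations for the results of the supporting and sensitivity analyses".

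**Missing diaries.** At 5% missing or less, "no imputation will be used, and the data will be analyzed using the Complete Case analysis set" (SAP 7.4). Above 5%, multiple imputation uses UUI values at baseline and months 1, 2, 3 and 6, with age, gender, history of pregnancy and BMI. A tipping-point analysis is also planned.

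**The concern.** The primary objective concerns response after 6 months of tibial neuromodulation. A subject shown by diary not to have responded, who then starts a drug or another advanced therapy and improves on it, can enter the numerator as a success of the device. The protocol generates the information that this subject was a non-responder, and the primary rule does not use it.

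The trial has one arm and a fixed goal. Compared with failure scoring, diary-only scoring can only raise the responder count, and no concurrent control would show the same shift. SAP 7.9.1.1 places the 40% goal between expected results for medications and for sacral neuromodulation, so response obtained with either of those blurs the comparison.

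Two smaller matters follow. The documents give two different medication windows for the same analysis. And a subject who moved to an advanced therapy and has no 6-month diary is either dropped or imputed as though no treatment had been added.

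**Working it through.** **Inputs from the documents:** n = 121, goal 40%, planned rate 55%, one-sided alpha 0.025, exact binomial test (SAP 6 and 7.9.1.1). **Assumed, because the documents give neither:** the number k of subjects who add treatment before month 6 (1, 3 or 6), and the conversion c, the share of them who then meet the 50% criterion (30% or 50%). Unless stated, all 121 subjects have a 6-month diary.

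**1. The plan's own figure.** P(X ≥ 59 | 121, 0.40) = 0.0313 and P(X ≥ 60 | 121, 0.40) = 0.0204, so success needs 60 responders (60/121 = 49.6%). Power is P(X ≥ 60 | 121, 0.55) = 0.9009, which agrees with the stated 90% or more.

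**2. Effect of diary-only scoring.** Let f be the expected response rate when treated subjects are scored as failures. The 121 − k untreated subjects then respond at rate u = 121f/(121 − k).

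- Failure-scored chance of success: P(Bin(121 − k, u) ≥ 60).
- Diary-only chance of success: P(Bin(121 − k, u) + Bin(k, c) ≥ 60).

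Example: with k = 3, c = 0.3 and f = 0.40, u = 48.4/118 = 0.410. The two chances are 0.0195 and 0.0302, a difference of 0.0107.

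Diary-only minus failure-scored chance of success:

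| k | c | f = 0.40 | f = 0.475 | f = 0.55 |
|---|---|---|---|---|
| 1 | 0.3 | 0.0032 | 0.0210 | 0.0084 |
| 3 | 0.3 | 0.0107 | 0.0640 | 0.0231 |
| 3 | 0.5 | 0.0193 | 0.1073 | 0.0367 |
| 6 | 0.3 | 0.0250 | 0.1305 | 0.0405 |
| 6 | 0.5 | 0.0501 | 0.2174 | 0.0592 |

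For 3 and 6 treated subjects, f = 0.475 gave the largest differences of the five rates tried (0.40, 0.45, 0.475, 0.50, 0.55). Only failure-scored counts of 57 to 59 (k = 3) or 54 to 59 (k = 6) can be carried across the line.

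A simpler calculation agrees. It gives every subject the rate 0.40 + kc/121. The chance of success is 0.0303 (k = 3, c = 0.3), 0.0389 (3, 0.5), 0.0438 (6, 0.3) and 0.0687 (6, 0.5).

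**3. Missing diary.** The 5% rule allows 6 subjects to be dropped (6/121 = 4.96%; 7/121 = 5.79%). With 59 responders among 121 subjects, p = 0.031 and the goal is not met. Dropping 2 advanced-therapy subjects without a diary gives 59/119, p = 0.021, and the goal is met. Dropping only 1 changes nothing, because 60 responders are still needed at n = 120.

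**4. Power after the fix.** If the planned 55% means response without added treatment, power stays at 0.9009. If it includes responders on added treatment, power is P(X ≥ 60 | 121, 0.55 − kc/121):

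- k = 3: 0.8690 (c = 0.3) and 0.8442 (c = 0.5).
- k = 6: 0.8307 (c = 0.3) and 0.7697 (c = 0.5).

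**The case against.** **This is partly a choice of estimand.** The plan names intention-to-treat on the Full Analysis Set, and counting the diary as recorded is one consistent reading of it. What is missing is an explicit statement, with a reason, of how added treatment is handled. Failure scoring is pre-specified, so the result will be visible, and sensitivity analyses do not normally decide success. All of this stands. It does not remove the conflict with the protocol's own non-response diary.

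**A reader might infer that the type I error is inflated to between 3.0% and 6.9%.** The documents do not support that as a general statement. Those figures take failure-scored response as the target. For the diary-based proportion that the plan defines, the exact error is 0.0204. Failure scoring has its own bias, because it fails a subject who would have responded to the device alone by month 6.

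**The numbers may be very small.** Added treatment is prohibited, and subjects have failed, not tolerated or are contraindicated to OAB medication (protocol 9.3). With one treated subject the effect is slight. The 21.7-point figure needs 6 treated subjects, 50% conversion and the least favourable of the rates tried.

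**A reader might infer that missing diaries open a wide gap.** They do not. The example needs exactly 59 responders and at least 2 such subjects. When imputation applies, non-response in the month 1 to 3 diaries informs it, and the tipping-point analysis covers missing data in general.

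**Regulatory history.** The protocol's version 3.0 log attributes the 12-month restriction and the added sensitivity analyses to FDA feedback, before enrollment. That shows review of the design. It does not show endorsement of this scoring rule.

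**Conclusion.** The point holds as a worthwhile and inexpensive improvement to the primary analysis. Nothing in the primary rule prevents a subject from being counted as a device responder on added, prohibited treatment, and the rule that would prevent it cannot change the success decision.

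The size is unknown. Under the stated assumptions, and with failure-scored response as the target, the added chance of success runs from 0.3 to 5.0 percentage points at a failure-scored rate of 40%, from 2.1 to 21.7 points at 47.5%, and from 0.8 to 5.9 points at the planned 55%. It matters mainly for a result near 60 of 121: at exactly 60 responders, reclassifying one subject reverses the conclusion.

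The documents do not show that many subjects will add treatment, or that the plan leaves its analysis principle unnamed. The difference in medication windows is real and needs reconciling whichever rule is primary. We did not have the text of SAP 7.12 (changes to planned analysis), so we do not say that the difference is unacknowledged.

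**What to change.** In protocol 14.4.1 and SAP 7.9.1.1:

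- Apply the SAP's existing failure rule in the primary Full Analysis Set analysis. Any OAB medication in the 2 weeks before the 6-month diary, or an advanced therapy at any time from implant to the 6-month visit, makes the subject a UUI non-responder. State that the medication window also covers the diary days, since protocol 10.1 allows the diary to follow the visit.
- Keep the diary-only result as a sensitivity analysis.
- Use one medication window in both documents and report the other as a sensitivity analysis. The 2-week window matches the baseline washout.
- Score a subject who received an advanced therapy before month 6 and has no 6-month diary as a non-responder. Do not drop, impute or count that subject as missing for the 5% rule. A medication subject without a diary stays under the missing-data rules, because the medication window is tied to the diary.
- Check that the sources behind the 40% goal scored added treatment compatibly; the documents do not say.

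**Cost.** No new data are needed: the medication log and advanced-therapy records already exist (protocol 10.5). The change needs a protocol and SAP amendment with IRB and, as applicable, FDA approval (protocol 16.6). The version 4.0 log cites monitoring of screen failures, so enrollment had begun by then. Changing a primary rule in an open-label trial at that stage needs a clear justification, written before month-6 results are examined. The responder rate will be slightly lower, and some subjects who would have responded to the device alone will count as failures. Power falls below 90% only if the planned 55% includes responders on added treatment, for example to 86.9% with 3 treated subjects at 30% conversion.
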